6.5.1.3.1 Guidance for corticosteroids tapering for management of adverse events common to dabrafenib and trametinib

Reduce prednisone dose by 2.5 to 5.0 mg decrements every 3–7 days until physiologic dose (5 to 7.5 mg of prednisone per day) is reached. Consider completing tapering over a period of at least 4 weeks. Slower tapering of corticosteroids therapy may be recommended if the adverse event is not showing improvement.

6.5.1.3.2 Mandatory dose modifications and recommended clinical management guidelines for abnormal liver enzyme test

Guidelines for dose modification and management of abnormal liver enzyme functions considered to be related to study treatment by the investigator are provided in [Table 6-7](#).

In addition to the instructions below, subjects with normal baseline transaminases and bilirubin who experience sudden elevations even within Grade 1, should be monitored more closely.

Table 6-7 Mandatory dose modifications and recommended clinical management guidelines for abnormal liver enzyme test

Abnormal liver enzyme tests/hepatitis		
Grade	Recommended adverse event management guidelines	Mandatory dose modification requirements
Grade 2: AST or ALT >3× ULN to ≤ 5× ULN and/or bilirubin > 1.5× ULN to ≤ 3× ULN	
 Monitor hepatic laboratory tests more frequently (every 2-3 days) until returned to baseline values 	
 Interrupt, dabrafenib and trametinib until ≤ Grade 1, and then reinstate, dabrafenib and trametinib at the same dose level.

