Grade 3 or 4: AST or ALT > 5× ULN and/or bilirubin > 3× ULN	
 Monitor hepatic laboratory tests more frequently (every 2-3 days) until return to baseline values. Consider appropriate consultation* with hepatologist and liver biopsy to establish etiology of hepatic injury, if necessary If after 2-3 days new liver assessment shows worsening of laboratory test consider to initiate treatment with high dose steroids (1 to 2 mg/kg/day prednisone or equivalents) Add prophylactic antibiotics for opportunistic infections Start steroid taper as outlined in Section 6.5.1.3.1 if symptoms improve to Grade ≤1 If serum transaminase levels do not decrease 48 hours after initiation of systemic steroids, oral mycophenolate mofetil 500 mg every 12 hours may be given. Infliximab is not recommended due to its potential for hepatotoxicity 	
1st occurrence
 
 Interrupt dabrafenib and trametinib until recovery to ≤ Grade 1 or baseline 
 Reduce dabrafenib and trametinib to the next lower dose level per Table 6-5. Re-escalation of the subject's dose is recommended if criteria in Section 6.5.1.2 are met If no recovery to ≤ Grade 1 within 4 weeks, permanently discontinue dabrafenib and trametinib. 
2nd occurrence
 
 Interrupt dabrafenib and trametinib until ≤ Grade 1. 
 Reduce dabrafenib and trametinib to the next lower dose level per Table 6-5. Re-escalation of the subject's dose is recommended if criteria in Section 6.5.1.2 are met dose 
3rd occurrence
 
 Permanently discontinue dabrafenib and trametinib

*Rule out viral hepatitis and other potential causes of liver injury

Note: For additional information on follow-up of potential drug induced liver injury cases, refer to [Section 6.5.2](#).

6.5.1.3.3 Mandatory dose modifications and recommended clinical management guidelines for renal function alterations

Cases of renal insufficiency have occurred in adult patients receiving dabrafenib and the combination of dabrafenib and trametinib. Prior to start of study treatment, concomitant medications must be reviewed for the potential risk of inducing nephrotoxicity and concomitant medications may be modified if clinically possible.

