6.5.2 Follow-up for toxicities

6.5.2.1 Follow up on potential drug-induced liver injury (DILI) cases

Subjects with transaminase increase combined with total bilirubin (TBIL) increase may be indicative of potential DILI, and should be considered as clinically important events.

The threshold for potential DILI may depend on the subject's baseline AST/ALT and TBIL value; subjects meeting any of the following criteria will require further follow-up as outlined below:

- For subjects with normal ALT and AST and TBIL value at baseline: AST or ALT > 3.0 x ULN combined with TBIL > 2.0 x ULN
- For subjects with elevated AST or ALT or TBIL value at baseline: [AST or ALT > 2 x baseline AND > 3.0 x ULN] OR [AST or ALT > 8.0 x ULN], combined with [TBIL > 2 x baseline AND > 2.0 x ULN]

Medical review needs to ensure that liver test elevations are not caused by cholestasis, defined as ALP elevation > 2.0 x ULN with R value < 2 in subjects without bone metastasis, or elevation of ALP liver fraction in subjects with bone metastasis.

Note: (The R value is calculated by dividing the ALT by the ALP, using multiples of the ULN for both values. It denotes whether the relative pattern of ALT and/or ALP elevation is due to cholestatic ($R \leq 2$), hepatocellular ($R \geq 5$), or mixed ($R > 2$ and < 5) liver injury).

In the absence of cholestasis, these subjects should be immediately discontinued from study drug treatment, and repeat LFT testing as soon as possible, preferably within 48 hours from the awareness of the abnormal results. The evaluation should include laboratory tests, detailed history, physical assessment and the possibility of liver metastasis or new liver lesions, obstructions/compressions, etc.

1. Laboratory tests should include ALT, AST, albumin, creatine kinase, total bilirubin, direct and indirect bilirubin, GGT, prothrombin time (PT)/INR and alkaline phosphatase.
2. A detailed history, including relevant information, such as review of ethanol, concomitant medications, herbal remedies, supplement consumption, history of any pre-existing liver conditions or risk factors, should be collected.
3. Further testing for acute hepatitis A, B, C or E infection and liver imaging (e.g., biliary tract) may be warranted.
4. Additional testing for other hepatotropic viral infection (e.g., CMV, EBV, Adenovirus, HSV, HHV6, HIV), autoimmune hepatitis or liver biopsy may be considered as clinically indicated or after consultation with specialist/hepatologist.

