9.1 Discontinuation

9.1.1 Discontinuation of study treatment

Discontinuation of study treatment for a subject occurs when study treatment is stopped earlier than the protocol planned duration, and can be initiated by either the subject or the investigator.

The investigator must discontinue study treatment for a given subject if, he/she believes that continuation would negatively impact the subject's well-being.

Study treatment must be discontinued under the following circumstances:

- Disease relapse
- Unacceptable adverse event, including meeting stopping criteria as described in [Sections 6.5.1](#) and [6.5.2](#).
- Subject/guardian decision
- Pregnancy
- Use of prohibited treatment as per recommendations in [Section 6.2.2](#)
- Any situation in which study participation might result in a safety risk to the subject.

If discontinuation of study treatment occurs, the investigator should make a reasonable effort to understand the primary reason for the subject's premature discontinuation of study treatment and record this information.

Subjects who discontinue study treatment or who decide they do not wish to participate in the study further should NOT be considered withdrawn from the study UNLESS they withdraw their consent (see [Section 9.1.2](#)). **Where possible, they should return for the assessments indicated** in the assessment schedule. If they fail to return for these assessments for unknown reasons, every effort (e.g. telephone, e-mail, letter) should be made to contact the subject/pre-designated contact as specified in the lost to follow-up section (see [Section 9.1.3](#)). This contact should preferably be done according to the study visit schedule.

If the subject cannot or is unwilling to attend any visit(s), the site staff should maintain regular telephone contact with the subject, or with a person pre-designated by the subject. This telephone contact should preferably be done according to the study visit schedule.

After study treatment discontinuation, at a minimum, in abbreviated visits, the following data should be collected at clinic visits or via telephone/email contact (per assessment schedule in [Table 8-2](#) or [Table 8-3](#)):

- new / concomitant treatments including any radiotherapy, surgical procedure or new anti-cancer therapy
- adverse events/Serious Adverse Events
- survival status

The investigator must also contact the IRT to register the subject's discontinuation from study treatment.

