9.2 Study completion and post-study treatment

Following twelve months of treatment or early treatment discontinuation, no further study treatment will be made available to a subject. All treated subjects should have a safety follow-up call conducted 30 days after last administration of study treatment. The information collected is kept as source documentation. All SAEs reported during this time period must be reported as described in [Section 10.1.3](#). Documentation of attempts to contact the subject should be recorded in the source documentation.

Study completion is defined as 24 months after the first dose (Day 1) of the last subject enrolled, and any repeat assessments associated with this visit have been documented and followed-up appropriately by the Investigator, or in the event of an early study termination decision, the date of that decision.

Subjects will be followed on the study per the schedule of assessments (refer to [Table 8-1](#), [Table 8-2](#), [Table 8-3](#)). Each subject will complete their EoS visit 24 months after Day 1 of the last subject enrolled or at early withdrawal from the study, death, withdrawal of consent, or lost to follow-up.

Post relapse therapy will be permitted during the study in the Follow-up Period per Investigator discretion, but not provided or administered as study treatment.

The final OS analysis will be performed when the last subject completes their EoS visit (i.e. 24 months after LPFV). All available data from all subjects up to this cut-off date will be analyzed.

The study will be closed when all subjects have either died, withdrawn consent, are lost to follow-up, 24 months after Day 1 of last subject enrolled, or when the last EoS visit is completed, whichever occurs first.

In the event the study is terminated due to futility, study subjects currently on study treatment in the Treatment Phase and who are still deriving clinical benefit will be eligible to continue their adjuvant treatment (i.e. up to 12 months dabrafenib in combination with trametinib) through a locally established Novartis program.

10 Safety monitoring and reporting

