10.2.1 Liver safety monitoring

Please, refer to [Section 6.5.1.3.2](#).

All follow-up information, and the procedures performed must be recorded as appropriate in the CRF.

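### Table 6-7 orders restart after recovery for treatment-related combined AST/ALT and bilirubin elevations that Section 6.5.2.1 says must be discontinued, and states no exception (minor, patient safety)

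*Protocol*

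**What the plan says.** **Table 6-7 (Protocol 6.5.1.3.2)** applies to liver test abnormalities that the investigator considers related to study treatment. Each row is defined by AST/ALT and/or bilirubin, so a combined elevation belongs in it.

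- Grade 2 (AST/ALT above 3 to 5 x ULN and/or bilirubin above 1.5 to 3 x ULN): the mandatory column says to interrupt until Grade 1 or lower, "and then reinstate, dabrafenib and trametinib at the same dose level". There is no limit on the number of occurrences.
- Grade 3 or 4 (AST/ALT above 5 x ULN and/or bilirubin above 3 x ULN): at the first and second occurrence, interrupt and then "Reduce dabrafenib and trametinib to the next lower dose level per Table 6-5", with re-escalation recommended. Permanent stop comes at the third occurrence, or at the first if there is no recovery within 4 weeks.

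**Section 6.5.2.1** sets laboratory criteria for potential drug-induced liver injury (DILI). If they are met without cholestasis, "these subjects should be immediately discontinued from study drug treatment". Liver tests are then repeated, preferably within 48 hours, and other causes are looked for.

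**Section 9.1.1** lists the circumstances in which study treatment must be discontinued. One is "Unacceptable adverse event, including meeting stopping criteria as described in" Sections 6.5.1 and 6.5.2. Section 9.2 adds that after early treatment discontinuation "no further study treatment will be made available to a subject".

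**The link between the two rules** is a note under Table 6-7: "For additional information on follow-up of potential drug induced liver injury cases, refer to" Section 6.5.2.

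**The concern.** The same subject can satisfy a Table 6-7 row and the 6.5.2.1 criteria together. A site working from the column headed as mandatory would restart both drugs once the liver tests recover. A site working from 6.5.2.1 and 9.1.1 would not. Nothing in Table 6-7 says which instruction yields.

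The stake is re-exposure, after recovery, of a subject with possible drug-induced liver injury whom Section 9.1.1 says must stop. It also leaves a site out of line with one written instruction whichever it follows.

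**Working it through.** The plan gives no figure to reproduce on this point. The check compares threshold regions and actions, then sizes the overlap.

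**1. Do the criteria overlap?** For a normal baseline, 6.5.2.1 needs AST/ALT > 3 x ULN and total bilirubin (TBIL) > 2 x ULN. Any such pair already satisfies a Table 6-7 row:

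- Grade 2 overlap: AST/ALT > 3 to 5 x ULN with TBIL > 2 to 3 x ULN.
- Everything above either upper limit falls in the Grade 3/4 row.

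**2. Elevated baseline.** The 6.5.2.1 thresholds, in multiples of ULN with b the baseline value, are:

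- AST/ALT: min(max(3, 2b), 8). Section 5.1 requires AST/ALT < 2.5 x ULN, so 2b < 5 and the 8 x ULN alternative never binds. For b = 1.5, 2.0 and 2.4 the threshold is 3.0, 4.0 and 4.8.
- TBIL: max(2, 2b). For b = 1.2 it is 2.4, so the Grade 2 overlap is TBIL > 2.4 to 3. For b = 1.5 it is 3.0, where the Grade 2 row ends, so that overlap is empty from there upwards. For a Gilbert's syndrome subject with b = 1.8 it is 3.6, so only the Grade 3/4 row can conflict.

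**3. What does each rule order?** Two subjects with normal baseline and ALP 1 x ULN. Cholestasis needs ALP > 2 x ULN with R < 2, so neither has it.

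| Subject | R = ALT/ALP | Table 6-7 | 6.5.2.1 with 9.1.1 |
|---|---|---|---|
| ALT 4, TBIL 2.5 x ULN | 4 | Interrupt, restart at same dose | Discontinue |
| ALT 9, TBIL 3.5 x ULN, first occurrence | 9 | Interrupt, restart one level lower | Discontinue |

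The rules agree on the immediate stop. They also agree in the end where Table 6-7 itself stops treatment, or where the general rule in Section 6.5.1.2 does so because there is no recovery within 4 weeks.

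**4. Is the 6.5.2.1 stop permanent?** That section does not use the word. Permanence comes from three other places: the glossary defines study treatment discontinuation as a permanent stop; 9.1.1 makes the 6.5.2 stopping criteria mandatory, and 6.5.2 contains only 6.5.2.1; and 9.2 rules out further study treatment.

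**5. Would a site find the override?** Section 6.5.1.2 sends sites to Table 6-6, which for abnormal liver tests lists only 6.5.1.3.2 and Table 6-7. Section 10.2.1, on liver safety monitoring, points only to 6.5.1.3.2. The note under Table 6-7 does reach 6.5.2, but describes it as follow-up information.

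**6. How many subjects?** Protocol 1.1.1.6 reports three COMBI-AD subjects with ALT > 3 x ULN and bilirubin at least 2 x ULN, among 435 treated.

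- Rate: 3/435 = 0.690%; exact (Clopper-Pearson) 95% CI 0.142% to 2.002%.
- Projected to the 556 subjects in the SAP: 0.00690 x 556 = 3.8; limits 0.00142 x 556 = 0.8 and 0.02002 x 556 = 11.1.

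This count probably overstates the overlap. It uses at least 2 rather than above 2 x ULN, reports no cholestasis exclusion, and is not limited to events considered related. The same section says that confounding factors excluded all three from meeting DILI criteria. The documents give no frequency for the Grade 2 zone.

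**The case against.** The strongest reply is that the protocol already resolves this. Section 6.5.2.1 is the specific rule, Table 6-7 the general one, 9.1.1 makes the specific rule binding, and the note under the table names potential DILI cases and sends the reader to the right section. Much of this stands: read as a whole, the protocol has 6.5.2.1 govern. But the reader must assemble that from four places, against a column labelled mandatory. The protocol can put an overriding stop beside a table: a footnote to Table 6-18 places the uveitis discontinuation rule directly under the instruction that lets dabrafenib continue.

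A second reply is that discontinuation in 6.5.2.1 may mean a hold until the repeat test. The dosing tables often say permanently when they mean it, and 6.5.2.1 does not. This stands in part. The protocol's usual word for a hold is interrupt, and the glossary points to permanence. For findings that the repeat test does not confirm, or that have another cause, 6.5.2.1 does not state whether restart is allowed. A reader might infer that everyone who meets the laboratory criteria must be barred from restart, but 6.5.2.1 distinguishes these groups without settling their dosing, so a blanket bar would decide a clinical question that it leaves open.

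A third reply is that harm is limited. Both rules stop both drugs at once, related events must recover within 4 weeks, and confirmed cases without another cause are serious adverse events reportable within 24 hours. All true, but none of these forbids the restart.

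**Conclusion.** The inconsistency is real and minor. For treatment-related combined elevations that meet the 6.5.2.1 criteria without cholestasis, Table 6-7 orders a restart that 6.5.2.1 and 9.1.1 exclude, and no exception is written into the table. The conclusion rests on reading discontinuation as the glossary defines it.

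Two stronger readings are tempting and not supported. One is that Table 6-7 keeps such subjects on drug: it does not, because it interrupts both drugs immediately. The other is that about 4, or as many as 11, subjects with drug-induced liver injury would be re-exposed. Those figures project laboratory triggers from COMBI-AD, where none of the three cases met DILI criteria, and they assume that the COMBI-AD rate carries over to 556 subjects.

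No endpoint is affected; the primary composite counts only pyrexia outcomes.

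**What to change.** 1. Add to both Table 6-7 rows, and in place of the follow-up note: *For subjects meeting the 6.5.2.1 criteria without cholestasis, 6.5.2.1 takes precedence over this table: stop both drugs at once, and do not restart if the repeat test confirms the finding and no alternative cause is found.*
2. Have the sponsor state in 6.5.2.1 whether restart is allowed when the repeat test does not confirm the finding or another cause is identified.
3. Add a pointer to 6.5.2.1 in Section 10.2.1.

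The cost is one line in two table rows, one replaced note, one sentence in 6.5.2.1 and one cross-reference, made by amendment or site letter. No new assessments or data fields are needed. Item 2 requires a clinical decision from the sponsor.

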5.1 Inclusion criteria

Subjects eligible for inclusion in this study must meet **all** of the following criteria:

1. ≥ 18 years of age
2. Signed informed consent must be obtained prior to participation in the study.
3. Completely resected histologically confirmed cutaneous melanoma stage IIIA (LN metastasis >1 mm), IIIB, IIIC, IIID [AJCC (ed 8) *see appendix 16.1*] no more than 12 weeks, from last surgery, before Day 1
 - a. Subjects presenting with initial resectable lymph node recurrence after a diagnosis of Stage I or II melanoma are eligible.
 - b. Patients who have previously had Stage III melanoma at any time are not eligible
 - c. Recovered from definitive surgery (e.g. no uncontrolled wound infections or indwelling drains).
 - d. Complete nodal resection is not mandatory for microscopic (SNB) disease
 - e. Full therapeutic lymph node dissection (TLND) is required for macroscopic disease, as per established treatment guidelines.
4. V600E/K mutation positive using a validated local test
5. Eastern Cooperative Oncology Group (ECOG) Performance Status of 0-1
6. Subject has adequate bone marrow and organ function as defined by the following laboratory values without continuous supportive treatment (such as blood transfusion, coagulation factors and/or platelet infusion, or red/white blood cell growth factor administration) as assessed by laboratory for eligibility:
 - Hematological
 - Absolute neutrophil count $\geq 1.5 \times 10^9/L$
 - Platelet count $\geq 100 \times 10^9/L$
 - Hemoglobin ≥ 9 g/dL
 - Coagulation
 - PT/INR and PTT $\leq 1.5 \times$ ULN. Subjects receiving anticoagulation treatment may be allowed to participate with INR established within the therapeutic range prior to Day 1
 - Renal
 - Serum creatinine < 1.5 mg/dL
 - Hepatic

- Total bilirubin $\leq 1.5 \times \text{ULN}$ except for subjects with Gilbert's syndrome who may only be included if the total bilirubin is $\leq 3.0 \times \text{ULN}$ or direct bilirubin $\leq 1.5 \times \text{ULN}$
 - Aspartate transaminase (AST) $< 2.5 \times \text{ULN}$
 - Alanine transaminase (ALT) $< 2.5 \times \text{ULN}$
 - Albumin $\geq 2.5 \text{ g/dL}$
7. Left ventricular ejection fraction (LVEF) \geq lower limit of institutional normal (LLN) as assessed by ECHO or MUGA scan
 8. Able to swallow and retain oral medication and must not have any clinically significant gastrointestinal abnormalities that may alter absorption such as malabsorption syndrome or major resection of the stomach or bowels

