6.5.1.2 Other dose modifications and reductions

The following sections address the specific instructions for mandatory dose modifications and recommended management for AEs considered suspected to be related to study treatment. For subjects who do not tolerate the protocol-specified dosing schedule, dose interruptions or modifications are mandated in order to allow subjects to continue study treatment.

Three dose reductions for dabrafenib and two dose reductions for trametinib are permitted. If more dose reductions of dabrafenib and trametinib are required, the subject must be permanently discontinued from that specific study treatment. Dose modification steps for dabrafenib and trametinib in [Table 6-5](#) must be followed for the AEs presented in [Section 6.5.1](#).

Table 6-6 provides sections where detailed dose modification and management requirements for relevant AEs can be found. All AEs are to be graded according to NCI-CTCAE v4.03, unless otherwise specified. Investigators should refer to the current dabrafenib and trametinib local prescribing information for additional information regarding the background of each drug and the management of other AEs or potential safety-related issues not specifically mentioned in this protocol.

If treatment-related toxicities occur that are specific to combination treatment of dabrafenib and trametinib, then both treatments should be simultaneously dose reduced, interrupted or discontinued with the exceptions shown below:

Exception where dose modification is necessary for **only dabrafenib**:

- Uveitis (Table 6-18)

Exception where dose modifications are necessary for **only trametinib**:

- RVO (Table 6-18) and retinal pigment epithelial detachment (RPED) (Table 6-19)
- Left ventricular ejection fraction (LVEF) reduction (Table 6-15)

If a subject's dose of dabrafenib and trametinib has been reduced per the dose modification instructions, re-escalation of the subject's dose is recommended provided the following criteria are met:

- a period of 4 weeks of treatment has passed since restarting dosing at the lower dose level and there is no recurrence of the AE
- the subject is deriving clinical benefit

For dabrafenib and/or trametinib related adverse events: if following an interruption of dabrafenib and trametinib, an AE doesn't recover to \leq Grade 1 or baseline within 4 weeks, dabrafenib and trametinib must be discontinued.

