Grade 3: Severe symptoms; limits self-care ADLs; oxygen indicated	
 • CT scan (high-resolution with lung windows) • Clinical evaluation and laboratory work-up for infection • Consult pulmonologist • Pulmonary function tests-if < normal, repeat every 8 weeks until \geq normal • Bronchoscopy with biopsy and/or BAL if possible • Treat with intravenous steroids (methylprednisolone 125 mg) as indicated. When symptoms improve to \leq Grade 1, a high dose oral steroid (prednisone 1 to 2 mg/kg once per day or dexamethasone 4 mg every 4 hours). • If IV steroids followed by high dose oral steroids does not reduce initial symptoms within 48 to 72 hours, consider non-corticosteroid immunosuppressive medication (e.g., infliximab, cyclophosphamide, IVIG or mycophenolate mofetil). 	
 • Interrupt trametinib until recovery to Grade \leq1 or baseline. Dabrafenib may continue. • Once recovered, trametinib may be restarted at the next lower dose per Table 6-5. Re-escalation of the subject's dose is recommended if criteria in Section 6.5.1.2 are met • If no recovery to Grade \leq 1 or baseline within 4 weeks, permanently discontinue trametinib. Dabrafenib may continue.
Grade 4: Life-threatening respiratory compromise	Same as Grade 3	Same as Grade 3

6.5.1.3.7 Dose modification and management guideline for adverse events suspected to be related to dabrafenib and/or trametinib (other than Pyrexia)

For adverse events of special interest reported **only for dabrafenib and/or trametinib**, general guidelines for dose modification in [Table 6-11](#) should be followed for dabrafenib and trametinib.

In general, if an AE resolves to Grade 1 or baseline at the reduced dose level, and no additional toxicities are seen after 4 weeks of study treatment at the reduced dose, the dose may be increased to the previous dose level.

A dose reduction below 50 mg BID for dabrafenib or below 1 mg QD for trametinib is not allowed. If a dose reduction below 50 mg BID for dabrafenib is required, dabrafenib will be permanently discontinued but these subjects will be allowed to continue trametinib. If a dose reduction below 1.0 mg QD for trametinib is required, then trametinib will be permanently discontinued, but these subjects will be allowed to continue dabrafenib.

Table 6-11 General guidelines for dose modification for adverse events suspected to be related to dabrafenib and/or trametinib treatment

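### Table 6-7, Grade 3/4 liver abnormality, first occurrence: restart accepts a return to baseline but the 4-week permanent stop does not (minor; Gilbert's subjects only)

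*Protocol*

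**What the plan says.** Table 6-7 governs liver test abnormalities that the investigator considers related to study treatment. In its mandatory column, the Grade 3/4 row for a first occurrence gives two instructions:

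- Hold and restart: "Interrupt dabrafenib and trametinib until recovery to ≤ Grade 1 or baseline", then resume at the next lower dose.
- Stop: "If no recovery to ≤ Grade 1 within 4 weeks, permanently discontinue dabrafenib and trametinib".

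Two other sections bear on this cell. Section 6.5.1.2 has a general rule for treatment-related events: if, after interruption, an event does not recover to ≤ "Grade 1 or baseline within 4 weeks, dabrafenib and trametinib must be discontinued". Section 9.1.1 lists the reasons for which treatment must end, among them "Unacceptable adverse event, including meeting stopping criteria as described in" Sections 6.5.1 and 6.5.2.

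Eligibility (Section 5.1, criterion 6) limits AST and ALT to below 2.5 × ULN and total bilirubin to 1.5 × ULN or less. The one exception is for subjects with Gilbert's "syndrome who may only be included if the total bilirubin is" ≤ 3.0 × ULN "or direct bilirubin" ≤ 1.5 × ULN.

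**The concern.** The two instructions in the cell use different definitions of recovery. A subject who is back at baseline but still above Grade 1 has recovered under the first and not under the second. The stop line also disagrees with the general rule in Section 6.5.1.2. That section describes what follows it as specific instructions, so a site could reasonably let the table override the general rule.

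The literal reading cannot be undone. Section 9.2 provides no further study treatment after early discontinuation. An eligible subject whose bilirubin is back at its entry value would lose the rest of an adjuvant course that Section 1.1 credits with a hazard ratio of 0.47 for relapse or death. Another site could restart the same patient at a reduced dose. Any such stop would also count in the secondary rate of discontinuation due to adverse events (Table 2-1).

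**Working it through.** No figure in the plan needs reproducing. The check compares the highest eligible baseline for each analyte with the Grade 1 ceiling implied by Table 6-7, which is the lower edge of its Grade 2 band.

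**Step 1. Who can have a baseline above Grade 1?**

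| Analyte | Highest eligible baseline (Section 5.1) | Grade 1 ceiling (Table 6-7) | Can baseline exceed Grade 1? |
|---|---|---|---|
| AST, ALT | below 2.5 × ULN | 3 × ULN | No |
| Total bilirubin, no Gilbert's | 1.5 × ULN | 1.5 × ULN | No |
| Total bilirubin, Gilbert's | 3.0 × ULN, or higher if direct bilirubin ≤ 1.5 × ULN | 1.5 × ULN | Yes |

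In the first two rows, being at baseline implies being at Grade 1 or below, so the two wordings are equivalent. Only the third row separates them.

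**Step 2. Apply each rule to example subjects.** Values are illustrative, in × ULN total bilirubin, with AST and ALT not raised. The Grade 3/4 trigger is bilirubin above 3.

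| Case | Entry → peak → value within 4 weeks | Restart line met? | Table 6-7 stop, read literally? | Section 6.5.1.2 stop? |
|---|---|---|---|---|
| a | 1.5 → 3.2 → 1.5 | Yes | No | No |
| b | 2.5 → 3.2 → 2.5 | Yes | Yes | No |
| c | 3.4 → 4.2 → 3.4 | Yes | Yes | No |

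Case (a) shows no conflict; (b) and (c) do. Case (c) enters through the direct-bilirubin route and is less typical, because its baseline already lies in the Grade 3/4 band. Case (b) is enough to establish the point.

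**Step 3. Does the liver-injury rule settle it?** Section 6.5.2.1 has separate thresholds, introduced by "For subjects with elevated AST or ALT or TBIL value at baseline". They require total bilirubin above 2 × baseline and above 2 × ULN, together with raised AST or ALT. For (b) that is 2 × 2.5 = 5.0 × ULN; for (c), 2 × 3.4 = 6.8 × ULN. The peaks of 3.2 and 4.2 fall short and the transaminases are not raised, so this rule does not apply. It does show that the protocol elsewhere judges these subjects against their own baseline.

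**Step 4. Compare the other toxicity tables.** The Grade 3 pneumonitis row of Table 6-10 has the equivalent 4-week stop for trametinib with baseline included. Table 6-9 (Grade 2 and Grade 3, first occurrence), Table 6-10 (Grade 2) and Table 6-17 (Grade 3) mix the two wordings, but each has a sentence in the same cell accepting baseline within 4 weeks. Table 6-7 has no such sentence.

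**Step 5. The rest of Table 6-7.** The Grade 2 row and the second-occurrence hold both require Grade 1 or below before restart. A subject with an entry value of 2.5 × ULN may never reach that point.

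**The case against.** The strongest reply is that the two lines are sequential. The first defines recovery, baseline included, and the second says what happens if recovery fails. On that reading a subject back at baseline has already recovered and the stop line is never reached. Supporting text exists: the management column of the same row monitors liver tests until they return to baseline; Section 10.1.1 treats a condition present at consent as medical history; and the Grade 2 row of Table 6-10 uses the same short stop wording beside a sentence that accepts baseline. The stop line also errs towards caution. Finally, the SAP ties the primary cut-off to all 556 subjects completing 12 months of treatment or discontinuing, so an amendment after that point would protect no one.

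Much of this stands. The shorthand reading is plausible and is very likely what was meant, and a wording change helps patients only while subjects are on treatment. It does not remove the error. In Table 6-10 the clarifying sentence is in the cell; in Table 6-7 it is missing. A mandatory, irreversible stopping rule should not need other sections to show its meaning.

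It is also true that adding baseline leaves the absolute grade bands unchanged, so a subject such as (c) still sits in the Grade 3/4 band after restart. What keeps a stable Gilbert's value out of the table is the requirement that the abnormality be treatment-related, which the investigator must judge under either wording.

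**Conclusion.** The concern holds: the stop line is wrong as written, and the error is minor. It affects a subject only if all of the following are true: Gilbert's syndrome with entry total bilirubin above 1.5 × ULN; a treatment-related rise above 3 × ULN that does not meet the Section 6.5.2.1 criteria; and a return to baseline, but not to 1.5 × ULN or below, within 4 weeks. The documents give neither the number of subjects with Gilbert's syndrome nor the number with raised entry bilirubin, so no count can be derived; it must be very small. A bilirubin-driven stop does not enter the pyrexia composite, so the primary endpoint is unaffected. At most a few cases could be added to the secondary rate of discontinuation due to adverse events.

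The conclusion rests on taking Table 6-7's own bands as the grade definition and on reading the stop line literally.

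**What to change.** In Table 6-7, Grade 3/4 row, first occurrence, insert *or baseline* after ≤ Grade 1 in the 4-week stop line. Make the same insertion in the Grade 2 row and in the second-occurrence hold, so that an affected subject has a restart point that can be reached. The Grade 2 stop line of Table 6-10 could be aligned at the same time. That change is editorial only, because the cell already accepts baseline and exclusion criterion 12 bars a history of clinically significant or active pneumonitis.

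The cost is two words in three places, or four with Table 6-10, in a protocol amendment made while subjects are still on treatment. It needs no extra visits, tests or analyses, and no SAP change.
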